10.3.4. Program cost data collection

We will use the program costing approach described by Kim and colleagues (2014)²⁷ combined with standard cost weights derived from the analysis of Medicaid or other archival billing data sources, if needed. Detailed resource use for the interventions will be collected for both the intervention groups and the usual treatment group²⁸. These data will be assigned standard cost weights developed using the data collection framework provided by Kim and colleagues (2014)²⁷. We will use the individual site data collected by the Excel model from Kim, combined with study contract and expenditure records to estimate the intervention costs and of resource use differences by treatment. The Kim Excel model is a standardized instrument that is used to capture the economic cost treatment programs (e.g., personnel, facilities, supplies) to calculate a cost per visit or other type of service²⁷. Study case flow and expenditure data will be used to determine the average cost/subject for each service type, average cost per technology-related resource used, and overall cost of technology to be amortized over the interventions

in the study. We will examine the effect of software amortization and market uptake assumptions on the ICERs estimated by the model.

10.3.5 Qualitative exit interviews

Transcribed exit interviews will be analyzed thematically for both a priori and emergent themes using Dedoose qualitative data analysis software (or equivalent). We will follow similar analytic procedures used in Phase 1 in order to identify possible areas for program improvement in Phase 2 and to provide additional context for interpreting the intervention's quantitative results.

10.4 Missing Data

Several procedures will be used to conduct data analysis when data for either outcomes or covariates are missing. The first step will be to assess the extent and pattern of missing data. If data are missing for only a few cases, then data analysis will be conducted only on study participants with complete data. However, when such a strategy would result in loss of data from a substantial proportion of participants, or if this approach would lead to biased or inaccurate results, then some form of imputation will be performed. The form of imputation used will depend on the nature of the data that are missing. For example, data that are collected repeatedly might be imputed using the "last value carried forward" method; and in some instances, interpolation between neighboring points might also be used. When the primary endpoint is missing, one data analysis will be conducted using only cases with the endpoint. Subsequent analysis will be done where missing endpoints are imputed. Hot-deck imputation or regression imputation may also be used in this context.

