6.6 Six-Month Assessment

The final assessment should be conducted 6 months after study enrollment. However, the assessment may occur two weeks prior to or 30 days after the ideal final assessment time point. At six months, all participants will complete a third online survey and undergo a medical chart review to abstract VL data. If participants have had a viral load taken in the two months prior to their six-month follow up appointment, they can complete the six-month follow-up survey remotely and receive their follow-up incentive. If they do not have a VL result from the prior two months, they can still complete their survey remotely but will be asked to provide a blood sample to assess viral load within three months of completing the six-month survey. Participants will receive \$50 for completion. Participants must complete both their survey and have an eligible viral load (either through chart review in last two months, self-report, or blood sample within three months after survey) to receive their incentive.

Participants who miss their one and/or three-month follow up are eligible to complete their final six-month visit.

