10.2.3 RCT Power Considerations

Power and sample size. The sample size calculation is based on the primary aim examining a change in the probability of **viral load suppression** from baseline to six months of follow-up between the standard of care arm and each of the two intervention arms. Using data from previous work, we estimate the probability of viral load suppression to be 0.66 in each of the three trial arms at baseline, and a change in this probability to 0.88 in each of the two intervention arms at six months of follow-up. Assuming this absolute change of 0.22, a two-sided alpha level of 0.05, and 15% loss to follow-up over the six-month study period, we estimate we will need 66 participants in each of the 3 study arms (n=198) to achieve 80% power to detect this change in the probability of viral load suppression between SOC and the two intervention arms. While our sample size is not powered to detect a difference between the two intervention arms, precise estimates of the efficacy for each arm are critical for subsequent costing analyses.

Power calculations were performed using PASS v.13 software (NCSS, LLC. Kaysville, Utah).

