In addition to the main six-month CAI outcome (any CAI with a potentially susceptible partner in the last 3 months), we will conduct a separate analysis in which “potentially susceptible partner” is defined as a partner who is not known to be HIV-positive or taking HIV medications (including PrEP). Additionally, we will compare the intervention and control arms with respect to the number of CAI acts in the last three months according to partner HIV and PrEP status (known HIV-positive, HIV-negative and not on PrEP, HIV-negative and on PrEP, unknown HIV status). Finally, linear mixed models will be fitted to all continuous outcome measures (i.e., self-regulation, self-efficacy to disclose, disclosure outcome expectations, consequences of disclosure, and intentions to disclose) to estimate the relative change in mean response from baseline to 6 months between intervention and SOC groups. Before fitting all models we will look for balance between treatment arms to assess the success of randomization, and we will adjust for possible confounding variables to improve precision and validity where needed. In the event that loss to follow-up is differential across treatment arms, we will employ inverse probability weighting to correct for this selection bias. We will test hypotheses using the likelihood ratio test, and goodness-of-fit among models will be assessed using the likelihood-ratio test, AIC and BIC criteria. Intervention completion and acceptability will be assessed at 1 month, and sensitivity analyses will evaluate how our findings for primary outcomes are influenced when we account for observed intervention completion.

Transmission Model

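### Section 10.4 does not exempt the disclosure scores planned for linear mixed models, so it allows men with partial survey records to be dropped or filled in when the model could use what was observed

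*Combined protocol and SAP*

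**What the plan says.** Section 10.3.3 (RCT Secondary Analysis Plan) states that "linear mixed models will be fitted to all continuous outcome measures". It names five: self-regulation, self-efficacy, outcome expectations, consequences of disclosure and intentions. The target is the difference between arms in change from baseline to six months. The same paragraph adds inverse probability weighting if loss to follow-up differs by arm. It does not say that all observed visits will be used. Table 2 schedules the five scores at baseline and at 1, 3 and 6 months.

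Section 10.4 opens by covering missing outcomes and covariates alike, and it exempts no model. Its first branch reads "If data are missing for only a few cases, then data analysis will be conducted only on study participants with complete data". Its second branch applies when that would lose a substantial share of participants or give a biased result; some form of imputation is then to be performed. As an example, "data that are collected repeatedly might be imputed using the" last-value-carried-forward method, and interpolation is also allowed.

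Section 6.6 states that "Participants who miss their one and/or three-month follow up are eligible to complete their final six-month visit". Section 6.5 has the parallel provision for men who missed month 1.

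**The concern.** Neither branch of 10.4 describes the analysis that suits the planned models, which is a likelihood fit to whatever visits each man supplied. That fit needs no complete record and no filled-in value, and it is valid when missingness depends only on observed data. A man with baseline and six-month scores but no month-1 survey supplies exactly the contrast that 10.3.3 wants. Yet 10.4 can be read as removing him, or as filling in a visit that the model does not need.

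At stake are the precision and possibly the bias of the secondary outcomes closest to what the app is meant to change. Nothing elsewhere settles which section prevails.

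**Working it through.** **The plan's own figure.** Section 10.2.3 takes suppression as 0.66 in every arm at the start and 0.88 in both intervention arms at month 6, tests two-sided at 0.05, allows 15% loss, and concludes "we will need 66 participants in each of the 3 study arms (n=198) to achieve 80% power". With pooled variance, mean rate 0.77 and SOC staying at 0.66:

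n = [1.96·√(2·0.77·0.23) + 0.842·√(0.66·0.34 + 0.88·0.12)]² / 0.22² = 56.2, so 57 per arm.

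57/0.85 = 67.1, so 68, within 2 of the stated 66. With 66·0.85 ≈ 56 evaluable per arm, power is 79.8%. The sample size is in order. No figure is stated for the disclosure scores.

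**Assumptions for the disclosure scores (none is in the documents).** 66 per arm; SD 1; equal correlation of 0.5 or 0.7 between visits; SOC mean flat; intervention mean 0, 0.25, 0.40 and 0.50 SD at 0, 1, 3 and 6 months. Each setting had 1,500 simulated trials. The all-data fit was generalised least squares with a mean for each arm at each visit and known covariance. Results are given as correlation 0.5 / 0.7.

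**Complete participants only, missing at random by chance.** If each of three surveys is skipped independently with probability s, the share of men incomplete is 1 − (1 − s)³.

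| Pattern | Incomplete | SE, all visits | SE, complete only | Increase |
|---|---|---|---|---|
| 15% dropout | 15% | 0.185 / 0.145 | 0.189 / 0.148 | 2% / 2% |
| 5% skipping | 14% | 0.171 / 0.135 | 0.183 / 0.144 | 7% / 7% |
| 10% skipping | 27% | 0.177 / 0.138 | 0.204 / 0.154 | 15% / 12% |
| 15% skipping | 39% | 0.183 / 0.140 | 0.220 / 0.170 | 20% / 21% |

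Both estimates are unbiased in these rows. Only precision differs.

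**Last value carried forward, random 15% dropout.** The dropout probability per interval is 1 − 0.85^(1/3) = 0.0527. Men lost before month 1, month 3 and month 6 make up 5.27%, 5.00% and 4.73%, and their carried values fall short of 0.50 by 0.50, 0.25 and 0.10:

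bias = −(0.0527·0.50 + 0.0500·0.25 + 0.0473·0.10) = −0.044, or −8.7% of 0.50.

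The simulation agrees: 0.458 / 0.453, against 0.500 / 0.497 from the all-data fit. The sign depends on the assumed shape. In a separate simulation (correlation 0.6) with an effect fading from 0.5 to 0.2 SD, carrying forward overstated the six-month effect by 0.020, or 10% of 0.2.

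**Last value carried forward, skipped surveys.** If only month 1 or 3 is skipped, the six-month score is observed and kept. With a separate mean per visit and no gaps after filling, the six-month contrast is the difference in observed mean changes, so the filled values do not move it. With 5% skipping at every survey, month 6 included, the estimates were 0.497 / 0.491 against 0.502 / 0.497.

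**Dropout that depends on the previous score (true effect 0.50).**

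| Mechanism | All visits | Complete only | Carried forward |
|---|---|---|---|
| Intervention arm only (about 12% lost) | 0.51 / 0.50 | 0.48 / 0.49 | 0.40 / 0.42 |
| Opposite directions by arm (about 17% lost) | 0.50 / 0.50 | 0.44 / 0.46 | 0.29 / 0.36 |

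The all-visit fit holds. Complete-participant estimates shift by up to about 13%, and carried-forward estimates by about 16-41%.

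**The case against.** A reader might infer that 10.4 obliges the analyst to drop or carry forward every man who skips a survey, at a large cost. With 15% skipping at each survey, correlation 0.6 and a 0.4 SD effect, complete-participant analysis would cut power from 70% to 52%. The documents do not support that reading, for these reasons:

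- The complete-data branch is confined to a small amount of missing data and gives way when the loss is substantial or the result would be biased. At 39% incomplete it would almost certainly give way.
- The 15% in 10.2.3 is cumulative loss over six months, not a rate per survey. Taken that way, the cost is about 2%.
- Section 6.4 lets the one-month survey be completed up to 160 days late, so equal and independent loss of that survey is unlikely. Section 10.1.3 lists these outcomes at baseline, 3 and 6 months only; with two follow-ups even 15% skipping leaves 0.85² = 72% complete, not 61%.
- Complete data is not defined and could mean having baseline and month 6.
- Carrying forward is an optional example, not a rule.
- Section 10.3.3 already offers weighting for differential loss.

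All of this stands, and it limits the size. It does not remove the point. No threshold separates the two branches, and leaving the first leads to imputation rather than to the all-visit fit. For repeated data the named examples are both single-value fills. The weighting applies only when loss differs by arm and does not deal with skipped intermediate surveys.

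**Conclusion.** The point holds as a modest conflict between 10.4 and 10.3.3. Section 10.4 applies to the disclosure scores, exempts nothing, and allows handling that the planned models do not need when data are missing at random.

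In the range where the complete-data branch plausibly operates, the standard error rises by about 2-7%. About 20% would need 15% skipping per survey, where 10.4 would probably switch to imputation. Last value carried forward, if chosen, attenuates a growing six-month effect by about 8-9% under random 15% dropout, and by more when dropout depends on earlier scores. It does little when only intermediate surveys are skipped. These sizes rest on assumed SD, correlation, effect shape and skip rates, and on missing at random.

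A reader might also infer that the trial's main conclusion is at risk. It is not: these are secondary outcomes, none of the three hypotheses in section 2.3 rests on a disclosure score, and the binary viral-load analysis is untouched by this point.

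**What to change.** Add to section 10.4: *Outcomes analysed by linear mixed models are fitted by likelihood to every observed visit of every randomised participant, under missing at random, with no restriction to complete participants and no single-value imputation of outcomes. Any imputation of these outcomes is a sensitivity analysis.*

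Keep 10.4's provisions for missing covariates, which the added text does not replace, and keep 10.3.3's weighting for differential loss. A cross-reference in 10.3.3 would make clear which text governs.

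The cost is a short wording change. It needs no new data, no change in sample size and no new primary model, since the mixed models are already planned. Missing at random remains an assumption, which is why the sensitivity analysis should stay.

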10.3.3 RCT Primary Analysis Plan

The study is a multi-site randomized 3-arm parallel group, longitudinal trial. The primary analysis will be based on intention-to-treat principles where we assume that all participants have followed their randomized assignment. The primary outcome is the probability of viral load suppression at six months, defined as less than the lower limit of detection as per the laboratory at each clinical site. At baseline, the most recent viral load will be abstracted from participants' medical records, within a specified time window (per trial eligibility criteria). At six months, participants' most recent viral load will be abstracted if one is available in the 2-month window prior to the six-month follow-up visit; if none is available within that window, a blood draw will be done for the study to ascertain viral load, or participant can have viral load measure as part of normal care within three months after six-month visit. We will use a binomial regression model (with identity link) for the risk difference (RD) in 6-month viral suppression, comparing each of the intervention groups with the SOC group. Due to random assignment, we expect that the probability of viral suppression at baseline will be balanced between the intervention and control groups. However, if baseline differences occur by chance, we will use inverse probability of treatment weights to correct imbalances in baseline viral suppression. Additional baseline covariates may be included in the model to increase the precision of treatment effects. The treatment weights may be combined with censoring weights if loss to follow-up exceeds 15% or if there is evidence of differential censoring by treatment group.

All analyses will be conducted using R (R Foundation for Statistical Computing, Vienna, Austria).

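### The planned imputed analysis of six-month viral suppression has no rule for imputation uncertainty; multiple imputation would supply one at almost no cost

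*Combined protocol and SAP*

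**What the plan says.** Section 10.4 of the combined protocol and SAP begins by assessing how much is missing and in what pattern. Complete cases suffice if few values are missing. If many participants would be lost, "or if this approach would lead to biased or inaccurate results, then some form of imputation will be performed". For the primary endpoint it makes two commitments: "When the primary endpoint is missing, one data analysis will be conducted using only cases with the endpoint", and then "Subsequent analysis will be done where missing endpoints are imputed".

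The methods are given in permissive terms. Carrying the last value forward (LOCF) is an example: "data that are collected repeatedly might be imputed using the" LOCF method. Interpolation is possible in some instances. The section closes with "Hot-deck imputation or regression imputation may also be used in this context". It does not mention multiple imputation, pooling, a bootstrap or any other variance rule.

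Section 10.3.3 (RCT Primary Analysis Plan) adds related tools. If baseline differences arise by chance, "we will use inverse probability of treatment weights to correct imbalances in baseline viral suppression". These weights "may be combined with censoring weights if loss to follow-up exceeds 15% or if there is evidence of differential censoring by treatment group". Also, "Additional baseline covariates may be included in the model to increase the precision of treatment effects". Neither section says how weighting and imputation relate to each other.

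**The concern.** The imputed analysis is there to check, or correct, the complete-case result, so it should not bring in an error of its own. The named methods can do so in two ways.

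- **Hot-deck and regression.** If one filled-in data set is analysed as though all 66 outcomes per arm had been observed, the standard error is too small and the test rejects too often.
- **LOCF.** The standard error is about right, but the estimate can be biased. Viral load is measured repeatedly, so the LOCF example can apply to it. Where no 3-month value exists, baseline is carried. Section 4.1 lets that value date from up to 12 months before screening, so at the limit it is about 18 months old at the six-month visit. A participant in an intervention arm would then be scored on status before the intervention, which dilutes any effect.

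Interpolation has little use for a value at the final visit.

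**Working it through.** **Inputs.** From Section 10.2.3: suppression 0.66 at baseline and 0.88 at six months in each intervention arm, two-sided alpha 0.05, 80% power, 15% loss, 66 per arm. From Section 10.3.3: a risk difference (RD) for each intervention arm against SOC. Assumed, because the documents do not give them: SOC six-month rate 0.66; loss completely at random and equal by arm (10 of 66); probability of six-month suppression given baseline suppression 0.85 in SOC and under the null, 0.95 under the planned effect.

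**1. The plan's own sample size.** With a mean rate of 0.77, n = [1.96·√(2·0.77·0.23) + 0.842·√(0.66·0.34 + 0.88·0.12)]² / 0.22² = 56.2, so 57 evaluable per arm. Then 57 × 1.15 = 65.6, so 66, the stated figure (57/0.85 would give 68). With 56 evaluable, power is 79.8%. The figure reproduces.

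**2. Standard error when one imputed set is treated as observed (null, both rates 0.66).** Let v = 0.66 × 0.34 = 0.2244.

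- Reported SE, as if 66 were observed: √(2v/66) = 0.0825.
- True SE, hot-deck with donors from the same arm: √{2v[1/56 + (10/66²)(55/56)]} = 0.0950. Ratio 0.868; implied type I error 2[1 − Φ(1.96 × 0.868)] = 8.9%.
- True SE, regression-mean by arm: √(2v/56) = 0.0895. Ratio 0.921; implied type I error 7.1%.

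Simulated SEs agree: 0.0816 reported against 0.0955 true for hot-deck (about 15% too small), 0.0817 against 0.0899 for regression (about 9% too small), and 0.0888 against 0.0899 for multiple imputation (MI).

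**3. Simulated type I error.** Two arms of 66, Wald test of the RD, 40,000 trials per setting. MI used 20 imputations, pooled as T = W + (1 + 1/20)B, where W is the within-imputation and B the between-imputation variance. Ranges cover different seeds, variance formulas and use of baseline.

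| Method, 15% loss | Type I error |
|---|---|
| One hot-deck set, donors from the arm | 9.6-9.9% |
| One hot-deck set, matched on baseline suppression | 8.5-8.6% |
| One regression-mean set | 7.0-8.5% |
| Complete cases | 5.5-5.9% |
| MI | 5.4-5.7% |
| No missing data | 5.6% |

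The last row shows that the Wald test itself sits slightly above 5%. At 5%, 10% and 20% loss, arm-level hot-deck gives 7.0%, 8.1% and 11.1%; MI gives 5.7%, 5.5% and 5.2%. Varying the assumed link with baseline (0.70 to 0.95) leaves arm-level hot-deck at 9.5-9.6%, moves matched hot-deck from 9.2% to 6.7% and regression-mean from 7.4% to 6.1%, and leaves MI at 5.2-5.5%.

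**4. Baseline carried forward for every missing case, planned effect.** Intervention arm: (56 × 0.88 + 10 × 0.66)/66 = 0.847. SOC stays at 0.66. RD = 0.187. SE = √[(0.847 × 0.153 + 0.2244)/66] = 0.0733, so power = Φ(0.187/0.0733 − 1.96) = 72%; simulation gives 72-73%. Complete cases: SE = √[(0.88 × 0.12 + 0.2244)/56] = 0.0768, power = Φ(0.22/0.0768 − 1.96) = 82%. MI in simulation: RD 0.219, power 82-83%.

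**5. Price of MI.** Simulated 95% half-widths at the planned effect: MI 0.147, complete cases 0.149, single hot-deck 0.137. MI is 0.147/0.137 = 1.07 times as wide as the understated interval, and no wider than complete cases.

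**The case against.** The strongest reply is that the harm is conditional and secondary. The complete-case analysis comes first and its standard error is sound. The wording is permissive, and both hot-deck and regression can be run as multiple imputation. Under random loss MI barely improves on complete cases: power differs by about one point at most, in either direction, depending on the assumed link with baseline. All of this stands, and it limits the point to the follow-on analysis. It does not remove the point, because the plan commits to that analysis and leaves open a choice among methods whose type I error runs from about 5.5% to about 10%.

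Three stronger readings are tempting, and the documents do not support them.

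- **That the trial's main result would have a 10% false-positive rate.** That figure belongs to one imputed set analysed as observed. The text neither prescribes nor excludes this.
- **That the carried value would usually be baseline because 3-month values come only from charts.** Section 6.5.2 says chart, but the Clinical Samples entry of the Study Abstract and Section 5.4.3 also allow blood draw or results shared by the participant. No section says how often a 3-month value will exist. The RD of 0.187 is therefore an upper bound on the dilution at 15% random loss.
- **That complete cases would be biased.** This needs a loss pattern that the documents do not give. Section 10.3.3 also offers weights and covariates, and Section 10.4 calls for imputation where bias is expected, although the covariates and censoring weights are optional and the bias trigger has no criterion.

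**Conclusion.** The point holds for the imputed follow-on analysis of the primary endpoint, as a cheap improvement. The named methods come with no rule for imputation uncertainty. Used singly at the planned loss, hot-deck would reject a true null about 10% of the time and regression-mean about 7-8%. LOCF could cost up to about 0.033 of the RD and about nine points of power.

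These sizes rest on an SOC rate of 0.66, equal and completely random loss of 10 in 66, a Wald test and an assumed link with baseline. The arm-level hot-deck result hardly depends on that link. MI is valid when data are missing at random given the variables in the model. It does not deal with loss that depends on the unseen viral load.

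**What to change.** For the primary endpoint, replace LOCF, interpolation, hot-deck and single regression imputation in Section 10.4 with wording such as: *Missing six-month suppression will be multiply imputed (20 imputations) by arm and baseline suppression, with 3-month viral load where available. The RD will be estimated in each completed data set and pooled with Rubin's rules.* The simulations used arm and baseline only; the 3-month value was not tested.

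In the same edit, state how the imputed analysis relates to the treatment and censoring weights in Section 10.3.3.

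A tipping-point analysis, with the shift varied by arm, may be added as a sensitivity analysis for data not missing at random. It is not easy to pass. With 49/56 against 37/56 observed and 10 missing per arm, 40 of the 121 possible combinations lose significance. For example, 3/10 against 5/10 gives 52/66 against 42/66: RD 0.152, SE 0.0777, p = 0.051.

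The cost is SAP wording and modest analysis work. It needs no new data and no change to 66 per arm, and power stays within about one point of complete cases.
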